5.2. Number of Patients

Patients will be screened to achieve 300 randomized and 300 evaluable patients for an estimated total of 150 evaluable patients per treatment group. Approximately 10 providers will recruited for study feedback. To address potential retention loss (estimate 90% retention), we will target 330 patients to be recruited and consented to the study, completing the baseline assessment.

5.3. End of Study Definition

The end of the study will be when the last visit by the last study patient is completed.

5.4. Scientific Rationale for Pragmatic Study Design

Control is usual care, as that is what patients currently receive. We are doing a physician randomization instead of patient randomization because of the potential for contamination (the intervention is diffuse) and the inability to prerandomize patients before their clinic visit.

5.5. Justification for Dose

Not applicable.

6. Study Population

Patients will be screened for eligibility via telephone within 7 days of patient's clinic visit.

6.1. Inclusion Criteria

Patients are eligible to be included in the study only if they meet all of the following criteria at screening/enrollment:

All patients. regardless of study arm, must meet the following eligibility criteria:

- 1) Patient is age 18 and older
- 2) Patient is English speaking
- 3) Patient is primarily responsible for administering their own medication
- 4) Patient must have received a new or changed prescription for a product(s), identified by Eli
- Lilly and the study team, within 7 days of recruitment*
- 5) Patient must have access to the internet
- 6) Patient must have a patient portal account

*Eligibility criteria may include refills for study medications at ACCESS sites only for the following reasons:

- 1) We have learned 60% of the BPAS are considered ineligible at ACCESS primarily due to refills. To meet BPA volume and milestone goals, Lilly USA and the study team will expand eligibility critiera for refills at these sites only.
- 2) ACCESS patients do not have the appropriate equipment to at home to monitor health status (for ex. glucose monitor) thus the majority of patients are seeing their doctors to only refill medicines during the COVID-19 pandemic.

Providers must meet the following eligibility criteria:

1) Provider working at a study site during study dates.

Type of Patient and Disease Characteristics

We will be recruiting patients who have been prescribed at least one of our target medications.

Informed Consent

Patients must be able and willing to give written informed consent.

6.2. Exclusion Criteria

Patients will be excluded from study enrollment if they meet any of the following criteria at screening/enrollment:

- 1) Severe, uncorrectable vision
- 2) Severe hearing impairments
- 3) Severe cognitive impairment
- 4) No access to the internet or patient portal account

Adults unable to consent, individuals under the age of 18, and prisoners will be excluded from this research.

For many patient characteristics, we will be able to ascertain differences between those participating and those who refuse to be included in the study, to determine potential bias. Additionally, research teams at both sites will limit recruitment of patients prescribed Metformin to 50 patients per site and will only recruit those with a new prescription. This quota has been set in place to ensure adequate representation of other study drugs with less volume compared to Metformin.

6.2.1. Medical Conditions

Not applicable.

6.2.2. Lifestyle Restrictions

Not applicable.

6.3. Screen Failures

Eligibility screening will take place before the written informed consent. Verbal consent will be obtained to ask screening questions. Individuals who do not meet the criteria for participation in the study (screen failure) may be rescreened and invited to participate a second time if they are prescribed a study medication at a different time. Intervals will vary and will depend on the date on which the medication was prescribed.

7. Treatments

7.1. Treatments Administered

This pragmatic study involves a comparison of intervention administered with standard of care in routine care.

Study Arms.

Usual Care: For this study, current usual care includes 1) variable provider counseling without any EHR notifications or counseling support; 2) variable distribution of print medication information materials, including FDA Medication Guides in clinics and variable distribution in pharmacies; and 3) limited or variable active surveillance of medication use post-visits.

Intervention: EMC² Strategy: There are several components that will be embedded into the workflow via EHR/patient portal platforms, mostly automating their implementation. Following patient movement through a provider visit, the following 6 activities will occur:

- 1. *Physician Medication Alert:* If a prescribing physician attempts to place a new order or change to an existing study medication prescription, an EHR-generated alert will notify the provider that the medication requires patient counseling. Physicians can opt to ignore this alert.
- 2. *Provider Counseling Support:* Content from the 1-page, Med Guide Summary will appear on the screen, if selected by the provider, to orient and inform provider-patient discussion.
- 3. Automated Delivery of Med Guide + Summary: When patients leave an encounter, the medication order in Epic will automatically cue printing of both the 1-page, health literate Med Guide Summary for study medications and a full Med Guide, if applicable (latter is required by FDA for certain medications only, the former designed to enhance comprehension). If the medication was ordered during a telemedicine encounter, the Med Guide Summary will automatically populate in the patient portal.
- 4. Follow-Up Portal Questionnaire: Within 1 week post-visit, patients will receive an automated email prompting them to log on to the patient portal. Patients' will be asked to fill out a short set of questions related to medication adherence, and other medication-related concerns (i.e. cost, side effects). If patients have not completed the questionnaire within 2 days, another email reminder will be sent. The information submitted back by the patient will be stored in the EHR.

Content in question form and corresponding responses for the portal questionnaire will be revised from prior evaluation scripts and written by Drs. [name], [name], [name], and [name].

The addition of the patient portal will provide opportunities to have ongoing communications with their clinic, access to regimen-specific medication information, and to provide a feedback loop informing healthcare providers of safety and adherence-related behaviors and concerns.

- 5. EHR Inbox Message to Clinic: The results of the patient portal questionnaire will be sent back to the EHR, populating an inbox message notifying the nurse/clinic staff and/or physician if a patient has a medication risk alert, detailing the nature of the issue (i.e. education needed, adherence problem, side effect concerns, etc.). The system will be flexible and allow the clinic to specify actions to be taken according to their workflow preferences; the default plan is that patient contact will be undertaken by nurses/clinic staff involved with care management.
- 6. Clinic Counseling: If a problem/concern is flagged during the review of the portal questionnaire, there will be an expectation for a clinic staff member to respond to the concern by calling the patient. A general orientation to staff at the clinic will provide guidance on how to perform brief counseling based on each specific clinic protocol.

7.2. Treatment Regimens

Not applicable.

7.2.1. Packaging and Labelling

Not applicable.

7.2.2. Medical Devices

Not applicable.

7.3. Method of Treatment Assignment

As the EMC² Strategy includes changes to healthcare delivery, the intervention itself is diffuse and individual patient randomization is not feasible. Therefore, randomization will occur at the provider (specifically, prescriber) level (N= ~50 eligible clinicians). Specifically, prescribers will be randomized to study arm (EMC² Strategy or usual care) prior to the initiation of the study. As patients are enrolled in the study, they will be automatically assigned to either intervention or usual care arms based upon the initial assignment of their physician. This specific strategy of "turning on" an EHR intervention with physician or clinic level randomization has been previously approved by the IRB at Northwestern University for three other AHRQ funded grants [P01HS021141-01, 1U19HS021093-01 & 1R18HS017220-01]. To optimize the likelihood of obtaining similar populations in each study arm, physicians will be placed into 4 strata based on workload (full time vs. part time) and site and randomly assigned to one of the two arms with an equal number assigned to each arm within each strata.

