10.1. Sample Size Determination

The sample size for this pragmatic study was based on comparisons of the primary outcome of medication knowledge between the two arms (i.e., usual care vs EMC²) at the T2 interview. We expect patients in the usual care arm to score an average of 55.6% correct responses (SD=28.4) based on a previous study that tested comprehension of the FDA standard Med Guides to those to be used in this study(9). Enrolling 330 patients and estimating 90% retention at the T2 interview (N=300, 150 per arm, 6 per provider), we will have 80% power to detect a minimum difference of 9.4% between the EMC² and the usual care arm assuming a Type I error of 5% (improving from 55.6% to 65.0% or greater). An intra-class correlation coefficient (ICC) of 0.001 was used; we expect clustering of physicians to have minimal influence on outcomes. However, even if the ICC were higher (i.e. 0.01) we could still detect a difference as small as 9.6%.

With the sample size set by the primary outcome, we also report minimum detectable differences for medication adherence measures. We estimate 65% of the usual care arm to demonstrate proper use of their medications based on prior studies(1, 18). With similar assumptions described above, a sample of 300 participants would enable us to detect a minimum absolute difference of 14.4% between arms with an ICC of 0.001 and 14.7% with an ICC of 0.01. We expect participants in the usual care arm to score an average of 27.5 (SD=7.2) on the ASK-12 based on validation studies(15). Retaining 300 participants (150 per arm, 6 per provider) at the T2 follow-up interview we will have 80% power to detect a minimum difference of 2.4 between the EMC² and the usual care arm (improving from 27.5 to 25.1 or less) using an ICC of 0.001 and a difference of 2.5 (improving from 27.5 to 25.0 or less) and with an ICC of 0.10. While no cut-off indicating non-adherence is provided, the goal would be for patients to score below 22.5, the average score in patients who took medications exactly as directed in the ASK-12 validation studies(15). We could detect differences smaller than this with the proposed sample size. In addition, differences in subscale scores of 1.3 for behavior, 0.9 for health beliefs, and 1.0 for inconvenience/forgetfulness could be detected between arms assuming mean scores of 10.5 (SD=3.8), 8.1 (SD=2.7), and 8.9 (SD=3.0), respectively, in the usual care arm.

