10.3. Statistical Analyses

10.3.1. General Statistical Considerations

We will perform analyses to address each of the aims using SAS v9.4 (Cary, NC).

The proposed trial uses a cluster-randomized design where the prescribing physician is the unit of randomization. We will randomize providers (i.e. attendings and fellows) to one of two intervention arms (usual care, EMC2). To optimize the likelihood of obtaining similar populations in each, providers will be placed into strata based on their

roles (attending, fellow) and historical volume of study medications dispensed (high, medium, low) for attendings. Providers from each strata will be randomized and identities will be revealed after randomization is complete. Patients enrolling in the study are assigned to the study arm of the provider signing their prescription within the EHR.

Given the brief follow-up period, we anticipate ~90% retention at T2 interview. These estimates result in 330 patients recruited with an anticipated 300 patients (150 per arm) available for primary data analysis.

Effectiveness analyses will be conducted on the full analysis set. This set includes all data from all randomized patients completing the outcomes of interest according to the treatment the patients were assigned.

All tests of treatment effects will be conducted at a 2-sided alpha level of 0.05, unless otherwise stated.

Any change to the data analysis methods described in the protocol will require an amendment ONLY if it changes a principal feature of the protocol. Any other change to the data analysis methods described in the protocol, and the justification for making the change, will be described in the clinical study report (CSR). Additional exploratory analyses of the data will be conducted as deemed appropriate.

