10.3.2.2. Patient Characteristics

T1 assessment will include socio-demographics, social support, and health status, including number of comorbidities. We will also probe for medication concerns (i.e. about costs, side effects, risks) for patients who do not fill or are not taking their medicine.

Health Literacy. We will assess health literacy via the Newest Vital sign or three validated screening questions that assess health literacy skills.

Patient Motivation. The Consumer Health Activation Index (CHAI) assesses patients' 'activation' or motivation to participate in healthcare decisions and actions.

T1 patient characteristics will be compared by arm using t-tests and χ 2 tests, as appropriate. Any significant differences (p < .05) across study arms will be entered as covariates in models described below.

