10.3.3. Efficacy Analyses

10.3.3.1. Primary Analyses

Aim 1. Test the effectiveness of the EMC² Strategy, compared to usual care, to improve patient understanding and safe use of prescribed medications

Medication knowledge is the primary outcome of interest, and will be analyzed as a score ranging from 0-100 reflecting the percent of items correct for each medication. Associations between medication knowledge and potential confounders at the patient (socio-demographic characteristics, comorbidities, # and type of medications taken, new or changed prescription, previous history with side effects, literacy, and primary language) and medication (drug type, route of administration) levels will be examined. We intend to use generalized linear mixed models (GLMM) to account for the correlated nature of the data from patients prescribed medications from the same providers, specifying the identity link for the outcome of medication knowledge using PROC GLIMMIX in SAS (v.9.4). Treatment assignment will be the independent variable of primary interest and modeled as a fixed effect, and prescriber will be modeled as a random effect. We will also include fixed effects for any potential confounding

covariates noted in the descriptive studies. For all GLMM analyses, we will report point estimates and 95% confidence intervals, and the extent to which random effects suggest correlation of outcomes within prescribers.

Additionally, we will examine rates of missing data, and determine if there are any discernible patterns using GLMMs with a logit link function to predict the presence of missing data. Should we find significant predictors, we will use multiple imputation methods and present results as secondary analyses.

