10.3.3.3. Tertiary/Exploratory Analyses

Aim 3. Evaluate the fidelity of the EMC² Strategy to promote provider counseling, deliver patient Rx information, and inform providers of potential harms.

Compared to usual care, patients receiving the EMC² strategy will:

- 1) report higher rates and quality of provider Rx counseling
- 2) report higher rates of receipt of print Rx information

Appropriate bivariate analyses will be performed based on each outcome measure described below using t-tests, Wilcoxon Rank-Sum, or $\chi 2$ tests, as appropriate.

Provider Rx Counseling. We will ask patients (yes/no) whether their provider(s) (physician/nurse) counseled them on their prescribed medication. We will also ask adapted questions from the Health Literacy supplemental items of the Consumer Assessment of Health Providers Survey (CAHPS) to evaluate the extent and quality of physician verbal counseling.

Receipt of print Rx information. All patients will be asked whether they received any print Rx information at their appointment. We will further probe intervention patients to determine whether the health literate Med Guide Summary was specifically received and its perceived helpfulness. Additionally, we will also collect EHR data to determine whether the Med Guide Summary was printed with their after-visit summaries.

We will also examine completion rates of:

- 1) the EHR portal survey by patients in the intervention arm
- 2) clinic follow-up for patients identifying Rx concerns in the portal survey.

Completion of the EHR Portal Survey. Intervention patients will be asked (yes/no) whether they received the emails to visit the portal and if they completed the portal questionnaire. We will also confirm this by determining if portal questionnaire results were populated in the EHR.

Clinic follow-up for patients identifying Rx concerns. At each performance site, clinical liaisons will share with the study team what specific medication-related concerns that are self-reported by patients via the portal assessment might warrant follow-up. It is at the discretion of each clinical practice to choose how they will triage the information provided via the feedback from the EMC2 intervention, and as part of the study we will explore the frequency and nature of follow-up that occurred for various medication-related concerns by self-report and in the EHR.

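### Sections 7.3 and 10.3.1 give incompatible randomisation strata, the Aim 1-2 model carries neither set, and the exploratory Aim 3 arm tests ignore the prescriber

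*Combined protocol and SAP*

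**What the plan says.** **Strata.** Section 7.3 states that "physicians will be placed into 4 strata based on workload (full time vs. part time) and site", with equal numbers of prescribers per arm in each stratum. Section 10.3.1 describes the same randomisation with strata formed from "roles (attending, fellow) and historical volume of study medications dispensed (high, medium, low) for attendings". Both are current text, and neither is marked as replaced.

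**Aim 1 and 2 model.** In Section 10.3.3.1, treatment is "modeled as a fixed effect, and prescriber will be modeled as a random effect". Covariates come from a screen of "potential confounders at the patient (socio-demographic characteristics, comorbidities, # and type of medications taken, new or changed prescription" and further patient items, plus medication-level items (drug type and route). Section 10.3.2.2 adds a rule for T1 patient characteristics: "Any significant differences (p < .05) across study arms will be entered as covariates in models described below". Section 10.3.3.2 repeats the model for adherence. Workload, site, role and volume are not named in any of these places.

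**Aim 3.** Section 10.3.1 says: "The proposed trial uses a cluster-randomized design where the prescribing physician is the unit of randomization". Section 10.3.3.3 nevertheless says of the fidelity outcomes: "Appropriate bivariate analyses will be performed based on each outcome measure described below using t-tests, Wilcoxon Rank-Sum" or chi-square tests. Two of these outcomes, provider counseling and receipt of print information, are compared between arms. Portal completion and clinic follow-up concern intervention patients only.

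**Clustering.** Section 10.1 says: "An intra-class correlation coefficient (ICC) of 0.001 was used; we expect clustering of physicians to have minimal influence on outcomes". It uses 0.01 as the sensitivity value for knowledge.

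**The concern.** There are three linked problems of unequal weight.

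1. **The two accounts of the randomisation cannot both be right.** A reader cannot report the allocation correctly, or fit the model that matches it, without knowing which scheme was used.
2. **The Aim 1-2 analysis does not reflect the stratification, whichever scheme it was.** If strata are balanced between arms and related to outcome, leaving them out keeps their variance in the error term. The arm estimate is not biased, but its standard error is too large. Site is a plausible example: refills are eligible at ACCESS only (Section 6.1).
3. **The Aim 3 arm comparisons treat patients of one prescriber as independent.** This errs in the liberal direction. Counseling is the prescriber's own behaviour, so clustering in that outcome is plausible.

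**Working it through.** **Comparing the two schemes.** Section 7.3: workload (2) x site (2) = 4 strata. Section 10.3.1: fellows, plus attendings at high, medium or low volume = 4 groups. The counts agree, so the count cannot tell them apart, and no factor is common to both. They cannot be merged either, because Section 7.3 fixes the number at four.

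**Inputs from the plan.** About 50 prescribers (7.3). From 10.1: 150 patients per arm, m = 6 per prescriber, SD 28.4 on knowledge, difference 9.4 points, ICC 0.001 and 0.01. Two-sided alpha is 0.05 (10.3.1).

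**Reproducing the plan's figure.** Design effect DE = 1 + (m-1) x ICC, which is 1.005 and 1.05. With 50 - 2 = 48 degrees of freedom,

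MDD = (t_0.975 + t_0.80) x 28.4 x sqrt(2 x DE/150)

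- ICC 0.001: 9.40 (plan: 9.4)
- ICC 0.01: 9.61 (plan: 9.6)
- No clustering: 9.38

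Both stated figures reproduce. Removing all clustering would improve the detectable difference by only 0.02 to 0.23 points, which bounds what stratum terms could gain.

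**Strata omitted, Aim 1.** A stratum effect is itself part of the between-prescriber ICC. Assume 34 prescribers at one site and 16 at the other, suggested by about 200 and 100 patients in the Synopsis. A site gap of d points then contributes ICC = 0.68 x 0.32 x d^2/28.4^2. An ICC of 0.001 allows d = 1.9 at most, and 0.01 allows d = 6.1. Simulated trials had exactly 6 patients per prescriber, arms balanced within strata, and total SD held at 28.4. In these rows all between-prescriber variance is due to site:

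| ICC | Method | Power at 9.4, strata omitted vs modelled | Type I error |
|---|---|---|---|
| 0.001 | cluster-mean t test | 80.1 vs 80.2% | no visible difference |
| 0.01 | cluster-mean t test | 78.8 vs 80.3% | about 4.4 vs 5.0% |
| 0.01 | REML, variance bounded at zero, between-prescriber df | 77.3 vs 78.4% | 3.6 vs 3.9% |

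Repeat cluster-mean runs at ICC 0.01 put the loss between 1.5 and 1.7 points. If only half of the between-prescriber variance is due to strata, the loss is about 0.8 points (cluster means) or 0.5 (REML).

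The role/volume scheme gives a similar answer. With an assumed 14 fellows and 12/12/12 attendings in equal steps, a range of 7.5 points corresponds to ICC 0.01, and power is 79.1 vs 80.6% (cluster means).

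Outside the plan's range for knowledge, a 10-point site gap plus a residual ICC of 0.001 gives ICC 0.028 and power of 76.1 vs 80.8%.

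**Aim 2.** For proper use (65% vs 79.4%) with a 10-percentage-point site gap (ICC 0.0096), a t test on prescriber proportions has power of 77.2 vs 78.9%. Fill, time to fill and ASK-12 were not simulated.

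**Prescriber ignored, Aim 3.** True type I error = 2 x (1 - Phi(1.96/sqrt(DE))), with m = 6:

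| ICC | DE | Type I error |
|---|---|---|
| 0.001 | 1.005 | 5.06% |
| 0.01 | 1.05 | 5.58% |
| 0.05 (assumed) | 1.25 | 7.96% |
| 0.10 (assumed) | 1.50 | 10.95% |

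Table 4 places these two outcomes at T1, where 330/50 = 6.6 patients per prescriber is the better count. The error is then 5.06, 5.65, 8.32 and 11.66%.

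**The case against.** **The consequences are small.** The firm defect is a wording conflict. For the primary outcome, the missing stratum terms cost little and in the safe direction, and Aim 3 is exploratory. This stands, and it is why the point does not threaten the trial's main conclusion.

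**The plan is partly open.** The Synopsis says GLMMs will test treatment effects, without excluding Aim 3, and Section 10.3.3.1 admits any confounding covariate. But Section 10.3.3.3 is the specific text for Aim 3 and names unclustered tests. The covariate screen lists patient and medication levels only. Strata are not barred, but they are not planned. Listed covariates such as new or changed prescription may absorb part of a site effect.

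**The simulations rest on assumptions.** The site and role/volume splits are not in the documents, and no workload effect was tried. The degrees-of-freedom method for PROC GLIMMIX is not stated. These limits stand.

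**Stronger readings that the documents do not support:**

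- A reader might infer that omitting strata can never make the test liberal. That was shown only with equal prescriber sizes and exact balance. Section 10.3.1 does not promise equal numbers per arm within strata, and volume strata imply unequal patient numbers.
- A reader might infer that adding strata restores exactly 5% error. With zero-bounded REML it moves only from 3.6% to 3.9%.
- A reader might call the Aim 3 inflation small because Section 10.1 uses low ICCs. Those ICCs are not given for counseling or print receipt.
- A reader might take 0.10 as a planned ICC, because Section 10.1 prints it for ASK-12. The 2.5-point difference attached to it fits 0.01 (2.44) and not 0.10 (2.91). It looks like a slip, but that is an inference.

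**Conclusion.** The point holds in three parts. The stratification schemes contradict each other and must be reconciled. No stratum term is planned for Aims 1 and 2. The Aim 3 arm comparisons ignore the randomised unit.

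For knowledge at ICC 0.001-0.01, omitting strata costs from nothing visible up to about 1.1 power points (REML) or 1.5 (cluster means). The upper figures require all between-prescriber variance to come from the strata, and apply to balanced designs under the assumed splits. The error is on the conservative side in the cases examined.

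For Aim 3 the direction is anti-conservative. The size is unknown because no ICC is given: slight at 0.001-0.01, about 8% and 11% at assumed values of 0.05 and 0.10.

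A reader might conclude that the primary analysis is invalid or materially underpowered. It is not: the prescriber is already a random effect there, and the plan's detectable differences reproduce. The change should be made because the randomisation must be described correctly and analysed as done, and because it costs little.

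**What to change.** 1. State the stratification actually used, in the same words, in Sections 7.3 and 10.3.1. Prescribers are randomised before the study starts, so this is a matter of record.
2. Add those strata as fixed effects to the Aim 1 and Aim 2 GLMMs. If site was not a stratum, a site term is optional. Name the degrees-of-freedom method.
3. In Section 10.3.3.3, replace the bivariate arm comparisons of counseling and print receipt with a cluster-adjusted analysis, such as a GLMM with a prescriber random intercept. Stratum terms and cumulative-logit links for ordinal items are optional here.

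**Cost.** No new data are needed. Four strata add three terms, so between-prescriber degrees of freedom fall from 48 to 45. If the strata have no effect, power falls from 80.1% to 79.9%. Aim 3 standard errors grow by sqrt(DE): x 1.002 to 1.025 at ICC 0.001-0.01, x 1.12 at an assumed 0.05 and x 1.22 at an assumed 0.10.
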